11.3.1. Analysis Populations

An intent-to-treat population will consist of all subjects randomized and will be analyzed as randomized All subjects who received study product will be included in the safety population and analyzed as treated. The PK analysis population will consist of all subjects who complete

ADM03820 injection and have sufficient evaluable PK samples for the estimation of PK parameters.

11.3.2. Demographics and Baseline Characteristics

Subject demographics and baseline characteristics will be summarized by dose cohort and control group.

11.3.3. Safety Analysis Plan

11.3.3.1. Adverse and Serious Adverse Events

AEs will be coded using Medical Dictionary for Regulatory Activities[®] (MedDRA). All AEs that occur after the initiation of study medication will be summarized using frequency counts and percentages. Summaries will be presented by dose cohort and control group. The following summaries will be presented for AEs and SAEs:

- Overall (i.e., regardless of severity or relationship to treatment)
- By CTCAE v5.0
- By relationship to study medication
- By MedDRA level hierarchy (system organ class and preferred term)

Unless otherwise specified, at each level of subject summarization in reporting the incidence of the AEs, a subject will be counted once if the subject reported one or more events. If more than one occurrence of an event is reported, the event of the worst severity or the worst-case relationship assessment will be summarized.

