3.2. Study Outcome Measures

3.2.1. Primary Endpoints

- The occurrence of Serious Adverse Events following administration of ADM03820 to the final follow-up visit.
- The occurrence of Adverse Events from administration of ADM03820 to the final follow-up visit.

²⁰ Eroshenko, N., Gill, T., Keaveney, M. Church, et al., Implications of Antibody-Dependent Enhancement of Infection for SARA-CoV-2 Countermeasures. *Nature biotechnology*. 05 June 2020. https://www.nature.com/articles/s41587-020-0577-1

• The occurrence of changes from baseline in physical examination, vital signs and clinical safety laboratory values following administration of ADM03820 to the final follow-up visit.

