5.2. Subject Exclusion Criteria

Subjects meeting any of the following exclusion criteria are not eligible for participation.

All must be answered no for the subject to be eligible for study participation

- 1. History of a chronic medical condition that would either interfere with the accurate assessment of the objectives of the study or increase the risk profile of the subject.
- 2. Subjects with cardiovascular disease
- 3. Subjects with diabetes
- 4. Subjects with pulmonary diseases such as COPD or asthma
- 5. History of severe allergic reaction of any type to medications, bee stings, food, or environmental factors or hypersensitivity or reaction to immunoglobulins.
- 6. A marked baseline prolongation of QT/QTc interval (e.g., repeated demonstration of a QTc interval >450 milliseconds)
- 7. Clinically significant abnormal electrocardiogram at screening.
 - Note: Clinically significant abnormal ECG results include but not limited to: complete left or right bundle branch block; other ventricular conduction block; 2nd degree or 3rd degree atrioventricular (AV) block; sustained ventricular arrhythmia; sustained atrial arrhythmia; two Premature Ventricular Contractions in a row; pattern of ST elevation felt consistent with cardiac ischemia; or any condition deemed clinically significant by a study investigator
 - Incomplete right bundle branch block is not exclusionary if there are no abnormal ECG findings and there is no clinical history or evidence on physical examination to indicate cardiac disease.
- 8. Positive serology results for HIV, HbsAg, or HCV antibodies
- 9. Febrile illness with temperature \geq 38°C within 7 days of dosing
- 10. Female subject is pregnant or breastfeeding
- 11. Donated blood or plasma within 56 days of enrollment
- 12. Known allergic reactions to any of the study product components present in the formulation or in the processing, as listed in the Investigator Brochure
- 13. Treatment with another investigational drug within 28 days of dosing
- 14. Treatment with a monoclonal antibody within 3 months of enrollment.
- 15. Positive serology results for SARS-CoV-2 antibodies (Not applicable for Cohort 5).
- 16. Positive results from a reverse transcriptase polymerase chain reaction (RT-PCR) test for SARS-Co-V-2

- 17. Receipt of antibody (e.g. TIG, VZIG, IVIG, IM gamma globulin) or blood transfusion within 6 months or within 5 half-lives of the specific product given

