- 18. Active drug or alcohol use disorder or dependence that, in the opinion of the investigator, would interfere with adherence to study requirements
- 19. Use of H1 antihistamines or beta-blockers within 5 days of dosing
- 20. Use of any prohibited medication within 28 days prior to screening or planned use during the study period
 - Note: Prohibited medications include immunosuppressives (except Nonsteroidal Anti-Inflammatory Drugs [NSAIDS]); immune modulators; oral corticosteroids (topical/intranasal steroids are acceptable); anti-neoplastic agents
- 21. Any specific condition that in the judgment of the investigator precludes participation because it could affect subject safety
- 22. Plans to enroll or is already enrolled in another clinical trial* that could interfere with safety assessment of the investigational product at any time during the study period
 - Note: Includes trials that have a study intervention such as a drug, biologic, or device
- 23. Is a study site employee or staff
 - Note: Site employees or staff include the Pis and sub-investigators or staff who are supervised by the PI or Sub-Investigators
- 24. Received an approved COVID-19 vaccine (subjects can receive an approved COVID-19 vaccine after completing their Day 90 visit. For Cohort 5, subjects who received a COVID-19 vaccine within 14 days prior to enrollment are excluded.

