8.3. Visit 3: Discharge from Unit (Day 2)

The subject is eligible for discharge 24 hours after the IM dosing is complete and after the following assessments have been performed and no signs of anaphylaxis have developed:

- Obtain vital signs (blood pressure, heart rate, respiratory rate, and oral temperature)
- Review and update concomitant medications
- Perform a symptom directed PE
- Obtain blood samples for the following:
 - PK measurement at 24 hours (± 2 hours)
 - MN
 - Serum sample to store for future use (if subject gave consent)
- Assessment of Aes and SAEs

- Remind the subject not to receive any drugs listed in section 6.8 for the duration of the study unless clinically indicated. If subjects receive necessary vaccines that are clinically indicated (e.g. tetanus after an open wound injury, influenza), they will be instructed to contact study staff immediately. Subjects may receive an approved COVID-19 vaccine after completing their Day 90 visit
- Counsel both men and women of childbearing potential on the avoidance of pregnancy
- Counsel all subjects on prevention of COVID-19
- Discharge subject and instruct on the next scheduled visit

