8.7.1 Adverse events

All AEs will be classified by Primary SOC and Preferred Term according to the MedDRA Version 23.0 or higher. The occurrence of AEs and SAEs following administration of ADM03820 to the final follow-up visit will be categorized as solicited adverse events, unsolicited adverse events and lab abnormalities. A summary table will be provided to summarize the frequencies and percentages of each category and overall by treatment group. Subsequent analyses will be conducted for each category, respectively, by severity, relationship to study medication, and by MedDRA level hierarchy (SOC and Preferred Term).

The occurrence of changes from baseline in physical examination, vital signs and clinical safety laboratory values following administration of ADM03820 to the final follow-up visit will be summarized descriptively by treatment group. AEs will be collected at Day 1 during and after dosing. Any medical condition that is present at the time that the subject is screened should be considered as baseline and not reported as an AE. However, if the condition increases in severity or frequency at any time during the study, it will be recorded

as an AE. Severity and relationship to the treatment will be assessed by investigator: severity is graded according CTCAE v5.0; relationship to the treatment is categorized as not related, possibly related, and definitely related.

Where a subject has the same adverse event, based on preferred terminology, reported multiple times in the treatment period, the subject will only be counted once at the preferred terminology level in adverse event frequency tables. Where a subject has multiple adverse events within the same system organ class in the treatment period, the subject will only be counted once at the system organ class level in adverse event frequency tables. Under both scenarios, the event of the worst severity or the worst-case relationship assessment will be used for summarizing safety endpoints.

AEs will be followed until resolution or stability even if this extends beyond the study-reporting period. Resolution of an AE is defined as the return to pretreatment status or stabilization of the condition with the expectation that it will remain chronic. Follow-up procedures, evaluations, and outcomes will be recorded on the subject's case report forms and will be presented using individual patient listings.

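### AE incidence runs to each cohort's final visit with no common window and no separation of post-vaccination events, although follow-up and COVID-19 vaccination rules differ between 600 mg and the lower doses

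*Protocol*

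**What the plan says.** **AE window.** The primary endpoint in Protocol 3.2.1 is "The occurrence of Adverse Events from administration of ADM03820 to the final follow-up visit". Protocol 11.3.3.1 adds: "All AEs that occur after the initiation of study medication will be summarized using frequency counts and percentages". SAP 8.7.1 uses the same period: "The occurrence of AEs and SAEs following administration of ADM03820 to the final follow-up visit". A subject counts once per level of summary, at worst severity or worst-case relationship. Tables are planned overall, by CTCAE grade, by relationship, and by system organ class and preferred term (SOC/PT). The protocol presents them by dose cohort and control group.

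**Follow-up.** Protocol section 4 ends Cohorts 1-4 with a telephone visit at Day 540 and Cohort 5 with the Day 365 visit.

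**Vaccination.** Exclusion 24 in Protocol 5.2 reads "Received an approved COVID-19 vaccine (subjects can receive an approved COVID-19 vaccine after completing their Day 90 visit", then adds a separate rule: "For Cohort 5, subjects who received a COVID-19 vaccine within 14 days prior to enrollment are excluded". Exclusion 15 is relaxed in the same way: "Positive serology results for SARS-CoV-2 antibodies (Not applicable for Cohort 5". The discharge instruction in Protocol 8.3 has no cohort limit: "Subjects may receive an approved COVID-19 vaccine after completing their Day 90 visit".

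**What is absent.** Neither document cuts off, flags or separately tabulates AEs after a vaccination, or adjusts AE percentages for length of follow-up. SAP 8.8.1 plans no subgroup analysis.

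**The concern.** Cohort 5 is the only 600 mg group, so its entry rule and its shorter follow-up are both tied to dose. A short-lived vaccine reaction in a subject with no other AE makes that subject an AE case. In a subject with a milder AE it can raise the worst grade. Such reactions can therefore enter the overall, severity and SOC/PT tables at different rates for 600 mg and the lower doses, for reasons unrelated to ADM03820.

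The change history makes unequal exposure plausible. Cohort 4 was added in June 2021 and Cohort 5 in July 2022, so a first vaccine series could fall within follow-up in the earlier cohorts and before entry in Cohort 5. The documents do not show that it did.

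At stake is how the final report's AE percentages are read across doses. There are no safety tests, so readers will compare the percentages directly. Each cohort has only 2 placebo subjects of its own. If the single control group pools placebo over cohorts, which the protocol does not state outright, 8 of its 10 subjects come from Cohorts 1-4.

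**Working it through.** **The plan's own figures.** Protocol 11.1 gives detection probabilities for 8 active subjects and a bound for 0 of 8 events. 1 - 0.85^8 = 0.7275 and 1 - 0.5^8 = 0.9961 match 0.728 and 0.996. The two-sided exact upper bound, 1 - 0.025^(1/8) = 0.3694, matches 0.369. All three reproduce, and this point does not affect them.

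**Time after Day 90 (from the documents).** Cohorts 1-4: 540 - 90 = 450 days. Cohort 5: 365 - 90 = 275 days. The ratio is 1.64. A common Day 365 cut-off would equalise follow-up, but 275 of its 365 days would still lie in the period when COVID-19 vaccination is allowed.

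**Follow-up length alone (assumed constant AE rate, no vaccine effect).** If a share p has had an AE by Day 90, the share by day t is 1 - (1 - p)^(t/90).

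| p by Day 90 | By Day 540 | By Day 365 | Gap |
|---|---|---|---|
| 0.1 | 0.469 | 0.348 | 0.121 |
| 0.3 | 0.882 | 0.765 | 0.118 |
| 0.5 | 0.984 | 0.940 | 0.045 |

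Gaps are taken before rounding.

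**Vaccine reactions (all inputs assumed).** Let b be the background AE incidence, u the share vaccinated on study after Day 90, and r the share of those reporting a reaction. Incidence is 1 - (1 - b)(1 - u r). With b and r equal across cohorts, the gap (lower doses minus 600 mg) is (1 - b) × r × (u in Cohorts 1-4 minus u in Cohort 5). With r = 0.6:

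| u, Cohorts 1-4 | u, Cohort 5 | b | Gap | Subjects per 8 |
|---|---|---|---|---|
| 0.5 | 0.5 | any | 0 | 0 |
| 0.5 | 0.2 | 0.3 | 0.126 | 1.0 |
| 0.5 | 0.2 | 0.6 | 0.072 | 0.6 |
| 0.5 | 0.2 | 0.9 | 0.018 | 0.1 |
| 0.8 | 0.3 | 0.3 | 0.210 | 1.7 |
| 0.8 | 0 | 0.3 | 0.336 | 2.7 |
| 0.3 | 0.6 | 0.3 | -0.126 | -1.0 |

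The gap scales directly with r.

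**Same uptake rate, different windows.** Suppose every cohort is vaccinated at 0.5 per year after Day 90. Uptake is 1 - exp(-0.5 × 450/365) = 0.460 in Cohorts 1-4 and 1 - exp(-0.5 × 275/365) = 0.314 in Cohort 5. At b = 0.3 and r = 0.6 the gap is 0.7 × 0.6 × 0.146 = 0.061.

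**What a Day 90 table does.** COVID-19 vaccination is allowed only after the Day 90 visit, so if that rule is followed u is zero in every cohort. The observation period is also the same for all.

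**The case against.** A reader might infer that vaccine reactions do enter unequally, and that they will produce a false inverse dose response or hide a real increase at 600 mg. The documents do not support that. Cohort 5 may enter vaccinated but need not, and nothing bars its subjects from vaccination or boosters on study. The gap can be zero or reversed. It also shrinks as background incidence rises, and over 540 days with laboratory abnormalities counted, that incidence may be high.

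The consequence is also limited. Dose escalation, and the safety review before phase 2, use data through Day 8 (Protocol 4, 9.5.3 and 9.6.4), which vaccination after Day 90 cannot affect. Safety is descriptive and imprecise. For 8 subjects at 600 mg against 32 active subjects at lower doses, the standard error of a difference near 50% is √[0.25 × (1/8 + 1/32)] = 0.198, so most of the gaps above are within about one standard error.

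Some safeguards exist. The relationship tables partly separate vaccine reactions, but they depend on investigator attribution and leave the other tables unchanged. SAP Table 4 plans safety looks at Day 90 for Cohorts 1-4 and Day 60 for Cohort 5. These are early but unmatched, and no AE onset cut-off is stated. Individual listings and concomitant-medication tables would let a careful reader trace cases, but they yield no comparable percentage.

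These arguments limit the size and weight of the point. They do not supply a table in which AE percentages can be compared across doses.

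**Conclusion.** The point holds as a gap in the analysis plan. As written, the final AE percentages for 600 mg and the lower doses cover different lengths of follow-up and different vaccination rules, and no planned table removes either difference. Unequal follow-up alone gives a gap of about 5 to 12 points in the constant-rate examples. The vaccine contribution is unknown in size and direction. At b = 0.3 and r = 0.6, both assumed, it ranged from -13 to +34 points, the top value requiring no on-study vaccination at all in Cohort 5. No sample-size figure, escalation decision or primary endpoint definition is called into question. This is a cheap improvement to interpretation.

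**What to change.** In SAP 8.7.1, keep the full-period tables as the analysis of the primary endpoint and add:

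1. A supportive AE table by cohort and treatment, for events with onset up to the Day 90 visit in all cohorts, stated to be the table used when AE percentages are compared across doses.
2. A flag for AEs starting within a pre-specified window after any vaccine recorded as a concomitant medication, with the full-period AE table repeated without flagged events. A window of 14 days would serve, stated as a convention.

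Confirm that vaccination dates are captured. Protocol 6.8 records any drug used, but the concomitant-medication footnote in the schedule of events does not name vaccines. Note in the SAP that the Day 90 table is not free of all vaccines, because influenza and other indicated vaccines are allowed earlier (Protocol 8.1 and 8.3). The flag covers those too.

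The cost is two extra tables and one flag, with no change to trial conduct. The drawback is that the Day 90 table covers only part of follow-up; the full-period tables still show the rest.

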11.3.3.2. Additional Safety Analyses

Vital signs, physical examinations, and clinical laboratory values, including change from baseline, will be summarized by dose cohort and control group.

Descriptive summary statistics for laboratory data at admission (baseline value) and each applicable post-dose visit, including change from the baseline value, will be calculated. Descriptive summary statistics for vital signs at screening (baseline value) and each applicable post-dose visit, including change from the baseline value, will be calculated. Shift tables, showing individual subject changes from baseline will be presented for laboratory parameters using toxicity grading. Subjects with Graded values of vital sign and laboratory parameters will be identified in listings.

11.3.4. PK Analysis Plan

PK parameters will be estimated for total antibodies of ADM03820 as measured by enzymelinked immunosorbent assay (ELISA) for samples from Cohorts 1 and 2. PK parameters for each of the monoclonal antibodies of ADM03820 as measured by enzyme-linked immunosorbent assay (ELISA) for samples from Cohort 3 and 4 using noncompartmental methods in WinNonlin or a similar software package. Parameters will be estimated by dose cohort. Summary statistics will include the mean, median, coefficient of variation, and range. When evaluable, estimated PK parameters will include:

- AUC_(0-t): Area under the concentration time-curve to the last concentration above the lower limit of quantitation
- C_{max}: Maximum observed concentration
- T_{max}: Time of maximum observed concentration
- Kel: Elimination rate constant
- $AUC_{(0-\infty)}$: Area under the concentration time-curve extrapolated to infinity
- t_{1/2}: Terminal elimination half-life
- CL: Total clearance
- V_z: Volume of distribution

Additionally, multi-compartmental models will be considered based on inspection of concentration-time curves. If models are fit, base models will assume first-order elimination from the central compartment, and models will be parameterized in terms of clearance, volume of distribution and inter-compartmental rates. Standard objective goodness of fit measures will be used to determine the final model.

11.3.5. Immunogenicity

Immunogenicity will be measured by the development of antibody titers. The presence of ADA will be measured over the course of the post-injection period.

11.3.6. Missing values and outliers

All attempts will be made to collect all data per protocol. No imputation will be performed for missing values. Outliers identified during the PK analysis will be discussed in the analysis report.

12. SOURCE DOCUMENTS AND ACCESS TO SOURCE DATA/DOCUMENTS

The site will maintain appropriate medical and research records for this trial, in compliance with ICH E6(R2) GCP, Section 4.9, and regulatory and institutional requirements for the protection of confidentiality of subjects. As part of participating in a DOD-affiliated, or manufacturer-sponsored study, the site will permit authorized representatives of the sponsor(s), DOD, and regulatory agencies to review (and, when required by applicable law, to copy) clinical records for the purposes of quality assurance reviews, audits, and evaluation of the study safety and progress.

Forms for use as source documents will be derived from the electronic CRFs and will be provided by ICON. Additional source data are all information, original records of clinical findings, observations, or other activities in a clinical trial necessary for the reconstruction and evaluation of the trial. Examples of these original documents and data records include, but are not limited to, hospital records, clinical and office charts, laboratory notes, memoranda, pharmacy dispensing records, recorded data from automated instruments, copies or transcriptions certified after verification as being accurate and complete, microfiches, photographic negatives, microfilm or magnetic media, x-rays, and subject files and records kept at the pharmacy, laboratories, and medico-technical departments involved in the clinical trial. If data is recorded directly into the eCRF with no paper source, then that data should be listed as being a direct electronic data entry with no paper source available.

13. QUALITY CONTROL AND QUALITY ASSURANCE

Following a written DOD-accepted site quality management plan, the investigational site is responsible for conducting routine quality assurance and quality control activities to internally monitor study progress and protocol compliance. The PI will provide direct access to all trial-related sites, source data/documents, and reports for the purpose of monitoring and auditing by the sponsor, and inspection by local and regulatory authorities. The PI will ensure all study personnel are appropriately trained and applicable documentations are maintained on site.

Clinical monitors will verify that the clinical trial is conducted, and data are generated, documented (recorded), and reported in compliance with the protocol, GCP, and the applicable regulatory requirements. Clinical monitoring reports will be submitted to RGS.

ICON will implement quality control procedures beginning with the data entry system and generate data quality control checks that will be run on the database. Any missing data or data anomalies will be communicated to the site(s) for clarification and resolution.

14. ETHICS/PROTECTION OF HUMAN SUBJECTS

14.1. Ethical Standard

The investigator will ensure that this study is conducted in full conformity with principles of the Belmont Report: Ethical Principles and Guidelines for the Protection of Human Subjects of

Research of the National Commission for the Protection of Human Subjects of Biomedical and Behavioral Research (April 18, 1979) and codified in 45 CFR 46, 21 CFR 50 and 56, and ICH E6(R2); 62 Federal Regulations 25691 (1997), if applicable. The investigator's Institution will hold a current Federal Wide Assurance (FWA) issued by the Office of Human Research Protection for federally funded research.

